10 SAFETY ANALYSES

The safety analysis will be performed using the safety population. Safety parameters include adverse events, laboratory parameters, vital signs, and physical examinations.

For each safety parameter, the last assessment made prior to the first dose of study medication will be used as the baseline for all analyses for that safety parameter.

10.1 ADVERSE EVENTS

Adverse events will be coded using the latest MedDRA version.

10.1.1 Proportion of Subjects with TEAE

An AE (classified by preferred term) started during the treatment period will be considered a TEAE if it was not present prior to the first dose of study medication, or it was present prior to the first dose of study medication but increased in severity during the treatment period. For subjects who permanently discontinue roxadustat early or complete the treatment period (24 weeks) but decide not to participate in the extension treatment, all AEs that occur up to 28 days after the last roxadustat dose will be counted as a TEAE. For subjects who complete the treatment period and decide to participate in the extension treatment, an AE that occurs after the treatment period (Week 24/EOT) will not be counted as a TEAE.

The number and percentage of subjects reporting TEAEs will be tabulated separately by system organ class and preferred term; by system organ class, preferred term, and severity; and by system organ class, preferred term, and relationship to study medication. If more than one event occurs with the same preferred term for the same patient, the patient will be counted only once for that preferred term using the most severe and most related occurrence for the summarization by severity and by relationship to the study medication.

The distribution of TEAEs by severity and relationship to study medication will be summarized.

The incidence of common ($\geq 5\%$ of subjects) TEAEs, common non-serious ($\geq 5\%$ of subjects) TEAEs (excluding TESAE), TESAEs, and AEs leading to discontinuation of study medication will be summarized by preferred term and sorted by decreasing frequency. In addition, the incidence of deaths and SAEs with a fatal outcome (i.e., events that caused death) will be summarized separately by preferred term.

AE summaries are presented as a crude incidence rate and patient exposure year (PEY) adjusted incidence rate. The PEY-adjusted incidence rate, per 100 patient exposure years, is defined as the incidence of an event divided by 100 times the PEY which is defined as (last dose date – first dose date +1) divided by 365.25.

Listings of subjects with SAEs, adverse events leading to discontinuation, and those who died will be presented

Temporal profile of TEAEs of special interest may also be plotted showing the subjects in the y-axis and time to these TEAEs in the x-axis ([Appendix 4](#)).

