4. STUDY DESIGN

4.1. Description of the Study

[figure not shown]
This open-label single arm study is designed to evaluate roxadustat in maintaining Hb in ESRD subjects receiving in-center HD either after conversion from a stable ESA dose: ESA use ≥ 6 weeks prior to conversion to roxadustat dosing or as initial anemia treatment, in subjects with < 6 weeks of total ESA use prior to start of roxadustat dosing.

The study periods are:

- o Screening Period: Up to 6 weeks
- o Treatment Period: 24 weeks
- Post-Treatment Follow-Up Period: Subjects permanently discontinuing roxadustat, should have one final safety assessment (TEAEs and TESAEs) 28 days after the last roxadustat dose.

An extension of roxadustat treatment after 24 weeks may be offered to interested subjects within the context of this study protocol upon agreement of the study site until roxadustat is commercially available, or up to 1 year after completing the 24 weeks, whichever comes first.

Figure 2: Study Design Overview

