8.3. Procedures for Eliciting, Recording, and Reporting Adverse Events

8.3.1. Adverse Event Reporting Period

The study period during which all AEs and SAEs must be reported begins after informed consent is obtained and ends 28 days after the last study visit, except for pregnancy reporting (Section 8.3.6). AEs (non-SAE) reported during screening should be reviewed and captured under medical history, if applicable.

Adverse events will be followed until resolved, stable, or until the subject's last study visit or lost to follow-up. If an AE is not resolved or stabilized at the subject's last visit, it is up to the discretion of the investigator and/or study Medical Monitor to determine if further monitoring of the event is warranted.

Adverse events collected prior to dosing of study drug will be considered "non-treatment emergent" while those reported after the first dose of study drug and up to 28 days after the last dose of study drug will be considered "treatment emergent" and be assessed for relationship to study drug. If an AE starts on Day 1, the investigator must assess as to whether the AE started prior to or after the administration of study medication and record accordingly.

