2 STUDY DESIGN

[figure not shown]
This open-label single arm study is designed to evaluate roxadustat in maintaining hemoglobin (Hb) in ESRD subjects receiving in-center hemodialysis either after conversion from a stable ESA dose: ESA use \geq 6 weeks prior to conversion to roxadustat dosing or as initial anemia treatment, in subjects with < 6 weeks of total ESA use prior to start of roxadustat dosing.

The study periods are as follows:

- **Screening Period:** Up to 6 weeks
- **Treatment Period:** 24 weeks
- **Post-Treatment Follow-Up Period:** Subjects permanently discontinuing roxadustat, should have one final safety assessment (Treatment Emergent Adverse Events (TEAEs) and Treatment Emergent Serious Adverse Events (TESAEs)) 28 days after the last roxadustat dose.

An extension of roxadustat treatment after 24 weeks may be offered to interested subjects within the context of the study protocol upon agreement with the study site. Data listings for the extension phase will be generated upon database lock and will include serious adverse events (SAEs), concomitant medications related to SAEs, and hospitalization records related to SAEs.

Study Design Overview

Primary Efficacy Endpoint: • Proportion of subjects with mean Hb \geq 10.0 g/dL, averaged over weeks 16-24

Secondary Efficacy Endpoints: • Proportion of subjects with mean Hb between 10-12 g/dL, averaged from week 16 through week 24

Conversion subjects:

- Mean Hb change from baseline to average Hb from week 16-24

Subjects will be dosed three times weekly (TIW), except if a subject requires < 60 mg/week to maintain Hb levels, in which case dose frequency may be reduced in a stepwise fashion, e.g., to twice weekly (BIW), then once weekly (QW).

Initial Dose

Conversion from ESA to Roxadustat

The initial roxadustat dose is determined using a conversion table based on the subject's previous prescribed ESA dose in the last 4 weeks prior to enrollment (for Mircera®:in the last 8 weeks prior to enrollment) (Table 1.1).

Roxadustat treatment should start after the following intervals:

- Two days after stopping epoetin
- One week after stopping darbepoetin alfa
- Two weeks after stopping methoxy polyethylene glycol-epoetin beta (Mircera®)

If the converted initial dose exceeds the maximum dose of 3.0 mg/kg/dose then the next-lower dose step should be chosen as the initial dose.

Table 1.1. Conversion from ESA to Roxadustat

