8 TREATMENT AND MEDICATIONS

8.1 STUDY DRUG EXPOSURE

Exposure to study medication will be summarized in terms of treatment duration in weeks, which is calculated using the following formula: (the date of last medication taken - the date of first dose taken +1)/7.

Total weekly study drug exposure is defined as the total actual dose (in mg and mg/kg) of study drug administered within the week (windowed by 7-day period from Day 1).

Weekly exposure and total study drug exposure will be tabulated for the safety population.

Per administration amount and administration frequency will also be tabulated for the safety population.

Patient-Exposure-Year (PEY) is defined as (Last Dose Date – First Dose Date + 1)/365.25.

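### For extension subjects the SAP stops counting TEAEs at Week 24, but its person-time formula has no Week 24 limit, so exposure-adjusted TEAE rates come out too low if the formula is followed literally

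*SAP*

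**What the plan says.** **Extension.** Protocol 4.1 sets a 24-week treatment period and then provides: "An extension of roxadustat treatment after 24 weeks may be offered to interested subjects within the context of this study protocol". It lasts until commercial availability or for up to 1 year after the 24 weeks, whichever comes first.

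**Event counting.** Protocol 8.3.1 defines treatment-emergent events without reference to the extension. The words that set the window are "those reported after the first dose of study drug and up to 28 days after the last dose of study drug will be considered". SAP 10.1.1 has two rules:
- For early discontinuers, and for completers who decline the extension, "all AEs that occur up to 28 days after the last roxadustat dose will be counted as a TEAE".
- For completers who enter the extension, "an AE that occurs after the treatment period (Week 24/EOT) will not be counted as a TEAE".

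**Person-time.** In SAP 8.1, "Patient-Exposure-Year (PEY) is defined as" last dose date minus first dose date plus 1, over 365.25. SAP 10.1.1 repeats the formula for the exposure-adjusted AE rates, and SAP 5.4 defines treatment duration from the same two dates. None of these mentions Week 24.

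**Extension output.** SAP 2 plans listings of SAEs and of the concomitant medications and hospitalizations related to them. The SAP plans no tabulated AE incidence for the extension.

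**The concern.** A rate per unit of exposure is interpretable only if events and person-time cover the same window. Here an extension subject's events stop at Week 24/EOT, while under the written formula that subject's person-time continues to the last extension dose. The mismatch can act in one direction only: it adds person-time in which no event can be counted, so the rate falls.

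The SAP presents AE summaries both as crude incidence and as a PEY-adjusted rate, and the primary objective concerns safe as well as effective dosing. A PEY-adjusted rate that falls as more subjects continue treatment would understate risk, and would not be comparable with rates from studies that match the two windows.

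There is also a conflict of definition. An event in a subject still taking roxadustat after Week 24 is treatment emergent under Protocol 8.3.1 and not under SAP 10.1.1, and the SAP text does not present this as a change from the protocol.

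**Working it through.** The plan gives no figure for this point, so there is nothing to reproduce. The check has two parts.

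**1. Is a Week 24 limit written anywhere that governs PEY?**

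| SAP section | Subject | Week 24 limit stated? |
|---|---|---|
| 8.1, 10.1.1 | PEY | No |
| 5.4, 8.1 | Treatment duration | No |
| 8.2 | Concomitant medication, extension subjects | Yes |
| 9.2.1 | Transfusion-free subjects, censoring | Yes |
| 10.1.1 | TEAEs, extension subjects | Yes |
| 13.2.1 | EOS visit, extension subjects | Yes, but it is a visit label |
| 13.2.3, 13.2.8 | Missing last dose date | Refer to the treatment phase or the EOT/EOS visit, but only when the date is missing |

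So the SAP writes the limit where it wants one, and does not write it for PEY.

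**2. How far could the rate move?**

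Inputs from the documents: 300 subjects planned; main period 24 weeks = 168 days; extension up to 1 year; PEY = (last dose − first dose + 1)/365.25.

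Assumptions: all 300 complete 24 weeks; a fraction *u* enters the extension for a mean of *d* weeks. The documents give neither *u* nor *d*, so I use *u* = 10–100% and *d* = 13–52 weeks.

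One subject with a full extension:
- PEY ended at Week 24: 168/365.25 = 0.46
- PEY to last extension dose: (168 + 365)/365.25 = 1.46
- Ratio: 533/168 = 3.17
- Share of this subject's exposure after the event cut: 365/533 = 68%

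Whole study. The numerator is the same under both denominators, so it cancels:
- PEY ended at Week 24: 300 × 168/365.25 = 138.0
- PEY to last dose: 300 × (24 + *u·d*) × 7/365.25
- Uncapped rate ÷ capped rate: 24/(24 + *u·d*)

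The last column assumes, purely for illustration, 60 subjects with an event. The capped rate would then be 60/138.0 = 43.5 per 100 PEY.

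| Uptake *u* | Mean extension *d* (weeks) | Uncapped PEY | Rate ratio | Uncapped rate per 100 PEY |
|---|---|---|---|---|
| 10% | 13 | 145.5 | 0.95 | 41.2 |
| 25% | 26 | 175.4 | 0.79 | 34.2 |
| 50% | 26 | 212.7 | 0.65 | 28.2 |
| 50% | 52 | 287.5 | 0.48 | 20.9 |
| 100% | 52 | 437.0 | 0.32 | 13.7 |

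The extension makes up more than half of all exposure only if *u·d* exceeds 24 weeks: uptake above 24/52 = 46% at 52 weeks, or above 24/26 = 92% at 26 weeks.

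**The case against.** **The Week 24 cut is a deliberate and coherent choice.** The treatment period is 24 weeks, the extension is optional and needs site agreement, and no endpoint is tied to it. The SAP closes the main study at Week 24 in several places. This stands: a 24-week main safety analysis is defensible, and nothing here argues against it.

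**The SAP can be read as meaning a Week 24 last dose.** SAP 13.2.3 speaks of the last medication date in the study treatment phase, 13.2.8 imputes a missing last dose no later than the EOT/EOS visit, and 13.2.1 places EOS at the Week 24 visit for extension subjects. A programmer might therefore cap PEY. This stands in part. Those rules cover missing dates and visit labels, so they do not limit an observed last dose in the extension. The intention may be right, but the text does not say so.

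**A reader might infer that the extension adds nothing to the safety assessment, or that its non-serious events appear in no table or listing.** The documents do not support either. Extension SAEs are to be listed. SAP 2 says what the listings include, not that they include nothing else. SAP 1 puts table and listing specifications in a separate document. The SAP 10.1.1 listings of deaths and of AEs leading to discontinuation are not expressly limited to Week 24. What can be said is narrower: no AE incidence is tabulated for the extension.

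**A reader might also take 68% and the 3.17-fold ratio as study results.** They are ceilings for one subject who completes a full year. Without uptake and duration, no study-wide value can be given, only a range.

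**Conclusion.** The point holds as a mismatch between numerator and denominator. As written, the PEY-adjusted TEAE rates count events to Week 24 for extension subjects but let their dosing time run on, which biases the rates low. Over the assumed ranges the overall rate would be 95% to 32% of the rate with PEY ended at Week 24. This rests on a literal reading of the formula, on all 300 subjects completing 24 weeks, and on assumed uptake and duration. If PEY is in practice cut at Week 24, the bias disappears and only the missing wording remains. Crude incidence is not affected by the denominator problem.

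The conflict with Protocol 8.3.1 does not depend on any assumption: the protocol has no extension exception and the SAP does. It calls for reconciliation, and does not invalidate the 24-week analysis.

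The absence of a tabulated extension AE analysis is a lesser matter, closer to a reporting preference. The protocol's Schedule of Assessments (Table 4) shows no extension visits, so non-serious events may be collected less evenly there.

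**What to change.** 1. In SAP 8.1 and 10.1.1, state that for subjects entering the extension, PEY and main-study exposure end at the Week 24/EOT date at which TEAE counting stops. Apply the same limit to treatment duration in SAP 5.4.
2. Label the SAP 10.1.1 rule as the main-study TEAE definition. Either reconcile it with Protocol 8.3.1 or record it as a deviation from the protocol with the reason.
3. Optionally, add a supportive table of TEAEs and TESAEs over the whole exposure, from first dose to 28 days after last dose as in Protocol 8.3.1, with PEY taken over the whole dosing period. Using the full safety population avoids conditioning on having completed 24 weeks. A footnote should say that extension subjects are self-selected and that no extension visit schedule is shown for eliciting non-serious events.

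Items 1 and 2 cost a few sentences of SAP text and need no new data. Item 3 costs one table set at a later data cut, and its results would need cautious reading for the reasons in the footnote.

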5.3. Subject Discontinuation and Withdrawal

The subject is free to permanently discontinue study medication at any time, without prejudice to further treatment. Discontinuation from study medication is not the same as complete withdrawal from the study (i.e., withdrawal of consent).

Protocol FGCL-4592-096 A01

Subjects may withdraw consent and discontinue from the study at any time by discontinuing study medication and refusing to return for any form of follow-up without any prejudice.

A subject who decides to discontinue study medication will always be asked about the reason(s) to discontinue study medication and the presence of AEs (if any). These data will be ascertained and documented by the investigator and recorded in the eCRF as appropriate. Any subject discontinuing study medication will be followed up for 28 days after discontinuing study medication whenever feasible for purposes of adverse event reporting.

Reasons for permanent discontinuation of study medication:

- Subject's decision (subject no longer wants to continue study medication (i.e., withdrawal of consent)
- Investigator's decision that it is in the best interest of the subject to be withdrawn from the study
- Adverse events
- Significant noncompliance with study procedures, as determined by Investigator or Sponsor
- Lack of efficacy / Meets ESA withdrawal criteria
- Subject is lost to follow-up
- Subject got transferred to a different location/dialysis center
- Subject is no longer requiring dialysis due to kidney transplant
- Site terminated by the sponsor
- Pregnancy
- Death

Upon discontinuation from the study, both female subjects of childbearing potential and male subjects with partners of childbearing potential must continue to use a medically acceptable method of contraception for 1 week following the last study drug administration.

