8.2 PRIOR AND CONCOMITANT MEDICATIONS

The World Health Organization Drug Dictionary (WHO Drug) will be used to classify prior and concomitant medications by therapeutic class and generic name based on ATC code level 3. Prior medication is defined as any medication taken and stopped prior to the first dose of the study medication. Concomitant medication is defined as any medication taken between the day of first dose of the study medication and the day of last study medication date + 28 days. For subjects who complete the treatment period and decide to participate in the extension treatment, any medication taken after the Treatment Period (Week 24/EOT) will not be counted as concomitant medications for the main study, but will be listed for the extension period.

Medication start and end dates and times will be compared with the start date of study drug and classified as per [Table 4](#).

In case of partial or missing dates, comparisons will be made based on the level of detail available. For example, if start date of study drug is 04Jan2013, and a medication has a start date of Jan2013 but missing day, the medication will be classified as concomitant.

Table 4. Classification of Prior and Concomitant Medications

Start date \ End date	Before start of study drug administration	On or after start of study drug administration	Missing
Before start of study drug administration	Prior	Concomitant	Concomitant
On or after start of study drug administration	—	Treatment Emergent Concomitant	Treatment Emergent Concomitant
Missing	Prior	Concomitant	Concomitant

Both prior and concomitant medication usage will be summarized by the number and proportion of subjects. Subjects will only be counted one time in each unique ATC Class and generic name if multiple drugs are used by a subject.

Detailed analyses may be performed on prior and concomitant medications of special interests such as oral iron, blood pressure medications, and lipids medications.

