13.2.3 Missing Date of Study Medication

When the last date of study medication during the study treatment phase is missing, all efforts should be made to obtain the date from the Investigator. If it is still missing after all efforts, then the last dispensation visit date during the treatment period will be used in the calculation of treatment duration.

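### SAP 10.1.1 puts the 100 on the wrong side of the exposure-adjusted TEAE rate and, for subjects not entering the extension, counts events over 28 days that the denominator leaves out

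*SAP*

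**What the plan says.** **The rate.** SAP 10.1.1 presents AE summaries as crude incidence and as an exposure-adjusted rate: "The PEY-adjusted incidence rate, per 100 patient exposure years, is defined as the incidence of an event divided by 100 times the PEY". This is the SAP's only definition of the rate.

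**The denominator.** SAP 8.1: "Patient-Exposure-Year (PEY) is defined as (Last Dose Date – First Dose Date + 1)/365.25". Section 10.1.1 repeats this. Neither section adds follow-up after the last dose.

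**The numerator.** For subjects who stop early, or who complete 24 weeks without entering the extension, 10.1.1 states that "all AEs that occur up to 28 days after the last roxadustat dose will be counted as a TEAE". Protocol 8.3.1 uses the same 28 days. For extension subjects, "an AE that occurs after the treatment period (Week 24/EOT) will not be counted as a TEAE". The section counts subjects rather than events: "The number and percentage of subjects reporting TEAEs will be tabulated separately by system organ class and preferred term". Protocol 5.3 qualifies the tail for those who stop: "Any subject discontinuing study medication will be followed up for 28 days after discontinuing study medication whenever feasible for purposes of adverse event reporting".

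**Last dose in extension subjects.** PEY carries no written Week 24 cut. One is implied elsewhere. SAP 13.2.3 says that when the last dose date is missing, "the last dispensation visit date during the treatment period will be used in the calculation of treatment duration". SAP 8.2 writes the cut out for medications: "any medication taken after the Treatment Period (Week 24/EOT) will not be counted as concomitant medications for the main study".

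**A related place.** SAP 9.2.1 (time to first RBC transfusion) first runs time at risk for an untransfused subject to the last study visit. It then censors at the minimum of last dose, last visit, death and Week 24. The formula for transfused subjects has no last-dose limit.

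**The concern.** An exposure-adjusted rate is useful only if its unit is what the label says and if its events and person-time cover the same period. Here the formula does not produce the labelled unit. For one group of subjects the numerator also covers up to four weeks that the denominator omits. The size of that gap varies with how many completers enter the extension, so the rate partly reflects extension uptake. This matters mainly if the rates are set beside those of other studies.

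Section 9.2.1 has a similar fault. Under its second rule, a transfusion after last dose counts as an event, although untransfused subjects who stopped at the same time have already left the risk set.

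**Working it through.** The documents give no PEY total, event count or adjusted rate, so there is no figure of the plan's own to reproduce.

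**Inputs from the documents:** about 300 subjects (SAP 5.2); a 24-week treatment period (SAP 2); a 28-day TEAE tail outside the extension (SAP 10.1.1).

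**Assumptions:** 25% stop at 12 weeks; constant hazard; dosing time cut at Week 24; a complete 28-day tail unless stated otherwise. Extension uptake is varied.

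**1. Scaling.** Dosing time is 75 × 12 + 225 × 24 = 6,300 weeks, and 6,300 × 7 / 365.25 = 120.7 PEY. For 15 subjects with an event:
- by the label: 100 × 15 / 120.7 = 12.4 per 100 PEY;
- by the formula: 15 / (100 × 120.7) = 0.00124.

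The ratio is 100 × 100 = 10,000 for any count.

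**2. Window gap alone, counting events.** The ratio is event-window time over dosing time.
- One 24-week completer outside the extension: 196 / 168 = 1.167.
- One subject stopping at 12 weeks: 112 / 84 = 1.333.
- Pooled, nobody extends: (75 × 16 + 225 × 28) / 6,300 = 7,500 / 6,300 = 1.190.
- Pooled, half of completers extend: 7,050 / 6,300 = 1.119.
- Pooled, all extend: 6,600 / 6,300 = 1.048.

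**3. Counting each subject once**, which is how the section reads. Two effects now oppose each other. The tail raises the rate. Person-time that keeps running after a subject's first event lowers it, more so for common terms. The ratio to the true first-event rate is Σ(1 − exp(−h × window)) / (h × 6,300), where the weekly hazard h is solved to give the stated crude incidence. Example: at 5% with nobody extending, h = 0.002054, so 15 / (0.002054 × 6,300) = 1.159.

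| Completers extending | 5% | 20% | 30% |
|---|---|---|---|
| none | 1.159 | 1.062 | 0.993 |
| half | 1.090 | 0.999 | 0.934 |
| all | 1.021 | 0.936 | 0.877 |

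If no subject who stops early has the tail, the rows become 1.112, 1.014, 0.946 (none extending) and 1.042, 0.952, 0.888 (half).

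**4. Matching windows but letting person-time run past the first event** (nobody extends):
- person-time extended by 28 days: 0.974, 0.892, 0.834 (at 30%, 90 / (0.01438 × 7,500) = 0.834);
- events counted only to last dose: 0.977, 0.907, 0.856.

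At 20% and 30% these are 9–17% low, further from the truth than the plan as written. Stopping person-time at the first event gives 1.000.

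**5. Sampling error for scale.** A count of 15 has exact Poisson 95% limits of 8.40 to 24.74, which is −44% to +65%.

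**6. SAP 9.2.1.** In a simulation of 2 million subjects (assumed true Week 24 proportion 6.0%, stopping uniform over 24 weeks), the second rule gave 6.14%, 6.24% and 6.37% at 15%, 25% and 35% stopping with full 28-day follow-up. With half of those stopping followed it gave 6.04%, 6.14% and 6.22%. One end date for everyone gave 5.97–6.03%.

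**The case against.** **The scaling is a slip that nobody would code.** Largely right. The unit stands in the same sentence, and a rate of 0.00124 would be noticed at once. A reader might infer that the reported rates will be wrong by a factor of 10,000. The documents do not support that; they support only that the formula needs correcting.

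**Dividing TEAEs by dosing time is an openly stated choice.** Fair as far as it goes. Sections 8.1 and 10.1.1 agree on PEY, crude incidence stands beside the rate, and this is a single-arm study with no hypothesis testing (SAP 11). But the choice treats extension and non-extension subjects differently, and nothing tells the reader so.

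**The direction is not fixed.** Correct. It is tempting to say that the mismatch inflates the TEAE rates generally, or that 19% is an upper bound. Neither holds. With subjects counted once, the net error changes sign between rare and common terms. The 1.190 belongs to one scenario: 35% stopping at 8 weeks gives (105 × 12 + 195 × 28) / (105 × 8 + 195 × 24) = 6,720 / 5,520 = 1.217.

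**Extension dosing in PEY.** Because no cut is written, one might infer that up to a further year of dosing enters the denominator. SAP 2 limits extension output to SAE-related listings, SAP 13.2.1 sets the end of study for these subjects at Week 24/EOT, and SAP 13.2.8 bounds an imputed last dose by the EOT/EOS visit. The cut is implied and only needs stating.

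**Section 9.2.1 is a different endpoint in a different analysis set.** True. It is kept here as a separate, small item.

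**Conclusion.** The point holds and is minor. The written formula does not give the labelled unit, and nothing elsewhere in the SAP corrects it. For subjects outside the extension, numerator and denominator cover different time. On the stated assumptions the resulting rate is about 2–16% high at 5% incidence and about 1–12% low at 30%. Those figures rest on constant hazard, the assumed stopping pattern, a complete tail and unknown extension uptake. They are all smaller than the sampling error of a count of 15. Crude incidence, the efficacy results and the sample size are untouched.

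The two censoring statements in SAP 9.2.1 cannot both apply to a subject seen after last dose. The effect is slight: about 6.0% becoming 6.0–6.4% under the assumed stopping.

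**What to change.** **(a)** In SAP 10.1.1, define the rate as 100 × (number of subjects with the event) / (total person-years at risk).

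**(b)** Use one window for events and person-time. Run person-time from first dose to the earliest of: the first event; the end of the subject's TEAE window (last dose + 28 days, or Week 24/EOT for extension subjects); death; last contact. Stopping at the first event is part of the fix, as step 4 of the working shows.

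If dosing-time PEY is kept for comparability, count only events up to last dose, cut last dose at Week 24/EOT for extension subjects, and label the result as subjects with events per 100 PEY of dosing, not as a first-event rate. Post-dose TEAEs then drop out of this rate but stay in crude incidence.

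**(c)** In SAP 9.2.1, set one end-of-risk date for every subject and count a transfusion only if it falls on or before that date.

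**Cost:** SAP wording, a derived end-of-window date per subject and a first-event date per term. No new data are needed. Option (b) loses some comparability with studies that divide by dosing time.
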